Sample Size and Rationale	Approximately 300 subjects : Re-enrollment is not allowed. - According to similar study results in the past, the difference between N-acetylcysteine (NAC) inhalation and standard treatment in the total score of the investigator's symptomatic severity assessment can be judged as 0.3. In this study, the assumed difference was 1 and the assumed standard deviation was 2.6, conservatively taking the highest value. With the assumed intraclass correlation coefficient (ICC) of 0.005, significance level of 5%, and test power of 80%, the study was to have 6 clusters (study centers) per treatment arm with a total of 12 clusters and 20 subjects in each cluster. it is calculated, as a result, that 120 subjects will be required per treatment arm and 240 subjects in total. Withdrawal is estimated at 20%; therefore, the plan is to recruit 300 subjects in total to have 150 subjects per arm and 25 subjects in each cluster.
Cluster (study center) Selection criteria	① Medical institutions in Korea at the general hospital level ② An otolaryngologist should be available to conduct the study.

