	
12 medical institutions in Korea that meet the inclusion criteria are cluster-randomized (test sites : control sites =1:1). Information about randomization is disclosed to both investigators and subjects. This means both study center investigators and subjects will be aware of the purpose of this study as well as the result of randomization (whether the subjects will receive NAC inhalation or not) from the beginning of the study.
 
Investigators shall obtain voluntary consent for participation in this research from patients who visit their medical institutions with symptomatic acute rhinosinusitis within the study duration. Patients who provided a written consent for the use of their personal information and who satisfy inclusion/exclusion criteria will be given a study enrollment number and available data on these patients will be collected among the predefined study relevant data in the case reports until Day 14 (± 3 days) from the starting day of treatment.
 
<Follow-up observation schedule and the scope of data collection>
 
Data created during subjects' visit to study centers for treatment shall be collected in the case report form. Follow-up observation time points defined below refer to data collection time points. That is, investigators can freely determine patient visit schedules based on the subjects' medical conditions regardless of the follow-up time points defined in this protocol. However, all the data created during the study period and judged to be necessary in relation to this study can be collected in the case report form.
 
In case of various tests including laboratory tests, no separate tests are conducted for this observational research and only those with test results are collected. Following data shall be collected during the study period.
 
 • Demographics of the subjects. • Disease information: diagnosis and start date of symptoms; indications on acute bacterial rhinosinusitis; anterior rhinoscopy/nasal endoscopy test results (for follow-up observation: if available); radiological test results (if available); and, infection source test results (if available). • Past medical history and intercurrent diseases: Examination on intercurrent diseases such as immune deficiency-inducing diseases, chronic diseases including diabetes, lower respiratory diseases, and asthma. Review on anatomical anomaly (if available) that increases the risk of rhinosinusitis, history of sinusitis surgery, and smoking preference. • Recent drug administration: Medication status for use of systemic antibiotics/antifungal agents, immunosuppressants, antihistamine drugs, or steroid for the past 4 weeks. • Body temperature, body weight, height (Enrollment data only for height and weight) • Rhinosinusitis treatment information: information on standard treatment and/or NAC inhalation, surgical procedures (if performed, for example: sinus irrigation or sinuscopy) • Co-medication/procedures: information on other drug administration and surgical procedures during the study period. • VAS assessment: to be indicated on 100mm VAS by subject for overall symptomatic severity. • SNOT-20 (Sino-Nasal Outcome Test) assessment: to be filled-out by subjects. • Investigator's symptom assessment: investigator's assessment for treatment response where each symptom's severity is rated by the investigator.

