Statistical Analysis Methods	
Analysis of primary endpoints
 
Obtain descriptive statistics (average, standard deviation, median, minimum, quartile, and maximum) for the change in the total score* of the investigator’s symptomatic severity assessment by treatment group on Day 14 compared with each time point and baseline (Day 0). Paired t-test shall be used to check intra-group change difference and Two sample t-test shall be used to check inter-group change difference.
 
Also, the same analytic methods shall be used for each cluster (study center).
 
Present ICC, and the Mixed model shall be used to check inter-group difference of the change in the total score of the investigator’s symptomatic severity assessment in consideration of clusters.
 
* The total sum of the investigator’s symptomatic assessment scores (on nasal congestion, nasal/postnasal discharge, facial pain/sense of facial pressure, and reduction/loss of smell).
 
Analysis of secondary endpoints
 
 Change in the total score of the investigator’s symptomatic severity assessment (Day 0, Day 7) Obtain descriptive statistics (average, standard deviation, median, minimum, quartile, and maximum) for the change in the total score of the investigator’s symptomatic severity assessment by treatment group on Day 7 compared with each time point and baseline (Day 0). Paired t-test shall be used to check intra-group change difference and Two sample t-test shall be used to check inter-group change difference.

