	
If necessary, in addition, Repeated Measures ANOVA can be conducted to check inter-group difference taking into account of changes in the total score of the investigator's symptomatic severity assessment on baseline (Day 0), Day 7 and Day 14. Multiple regression analysis can also be performed to check factors that influence the change in the total score of the investigator's symptomatic severity assessment. For this, independent parameters may include demographics, baseline characteristics and clinical factors that can be selected in consideration of collected data or clinical characteristics.
 
 • Change in SNOT-20 scores (Day 0, Day 14) Obtain descriptive statistics (average, standard deviation, median, minimum, quartile, and maximum) for individual and total SNOT-20 scores by group on Day 14 compared with each time point and baseline (Day 0). Paired t-test shall be used to check intra-group change difference and Two sample t-test shall be used to check inter-group change difference. 
Analyses of safety data
 
 • Adverse drug reaction (ADR) incidence Present the number of subjects with ADR related to NAC inhalation, ADR incidence, 95% confidence interval for the incidence, and the number of ADR cases. Also, present the number of ADR cases by characteristic (severity, measures taken, progress, and etc.) • Serious adverse event/adverse drug reaction incidence Present the number of subjects with serious adverse event(s) and serious adverse drug reaction(s), their incidence, 95% confidence interval for the incidence, and the number of cases.
--	---

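### The only analysis that joins Day 0, Day 7 and Day 14 is an optional Repeated Measures ANOVA; a pre-specified longitudinal mixed model with a centre effect would be a cheap improvement

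*Combined protocol and SAP*

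**What the plan says.** All references are to the Protocol Synopsis in the combined protocol and SAP.

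- **Statistical Analysis Methods, secondary endpoints.** As an addition if needed, "Repeated Measures ANOVA can be conducted to check inter-group difference taking into account of changes in the total score" at Day 0, Day 7 and Day 14. The text gives no trigger for running it, no centre term, no covariance structure and no missing-data rule.
- **Statistical Analysis Methods, primary endpoint.** For the Day 0 to Day 14 change, "Two sample t-test shall be used to check inter-group change difference". The same section also requires the ICC to be presented and a mixed model that takes clusters into account for the change in total score. No missing-data rule is given here or elsewhere in the supplied text.
- **Sample Size and Rationale.** The design has "6 clusters (study centers) per treatment arm with a total of 12 clusters and 20 subjects in each cluster", with an "assumed intraclass correlation coefficient (ICC) of 0.005". "Withdrawal is estimated at 20"%, which takes the 240 required to 300 recruited.
- **Study Methodology.** Allocation is by centre and is known to investigators and patients. Available data are collected, and "investigators can freely determine patient visit schedules" according to the patient's medical condition, whatever the protocol's follow-up time points.

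**The concern.** There are two weaknesses, and they differ in weight.

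**Missing scores.** A classical Repeated Measures ANOVA keeps only patients with all three scores. The primary t-test and the primary mixed model take the Day 14 change as outcome, so a patient without a Day 14 score contributes nothing to either, even when a Day 7 score is on file. Because visits follow medical condition in an open study, whether a Day 14 score exists may depend on response and possibly on arm. If it depends on response differently in the two arms, a complete-case comparison is biased, and an ANOVA on the complete cases does not correct it.

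**Centre.** Centres were randomised. An analysis that treats patients as independent gives p-values that are too small, by an amount that depends on the ICC.

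At stake is whether the study's one longitudinal analysis can serve as a check on the Day 14 result, or only repeats its limitations.

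**Working it through.** **1. The plan's own figures.** Inputs from Sample Size and Rationale: "the assumed difference was 1 and the assumed standard deviation was 2.6", "significance level of 5%, and test power of 80"%, ICC 0.005, 20 evaluable patients per centre. Two-sided testing is assumed, since sidedness is not stated.
- n per arm before clustering = 2 × (1.960 + 0.842)² × 2.6² / 1² = 106.1
- Design effect = 1 + (20 − 1) × 0.005 = 1.095
- 106.1 × 1.095 = 116.2 per arm, or 5.81 centres of 20, rounded up to 6 centres = 120 per arm, 240 in total
- 240 / 0.8 = 300

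The figures reproduce. The withdrawal allowance leaves exactly the 240 required.

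**2. Ignoring centre.** For a two-group comparison of one value per patient, with 20 per centre, the actual type I error is 2 × [1 − Φ(1.96 / √DEFF)].

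| ICC | DEFF | Type I error |
|---|---|---|
| 0.005 (planned) | 1.095 | 6.1% |
| 0.01 (assumed) | 1.19 | 7.2% |
| 0.02 (assumed) | 1.38 | 9.5% |
| 0.05 (assumed) | 1.95 | 16.0% |

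A simulation of 12 centres of 20 agrees with these values. In the same simulation a t-test on centre means (10 degrees of freedom) stays at about 5%.

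**3. Loss of incomplete patients.** The documents do not give missingness by visit. Suppose 20% lack Day 14, and 10%, 20% or 30% of the rest lack Day 7 (assumed). Complete cases are then 300 × 0.8 × 0.9 = 216, × 0.8 = 192, or × 0.7 = 168. With the step 1 formula run in reverse and the design effect recomputed for 18, 16 or 14 per centre, power for a difference of 1 is 77%, 73% or 68%, against 81% at 240. This applies only to an analysis confined to patients with all three scores.

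**4. Complete-case bias, as a scenario.** Every input here is assumed, apart from the 2.6 and the 150 per arm:
- mean total scores 7, 5 and 3.5 at Day 0, 7 and 14, with SD 2.6 at each visit
- correlations 0.5 (Day 0–7), 0.4 (Day 0–14) and 0.6 (Day 7–14)
- no centre effect
- log-odds of a missing Day 14 score = −1.75 + b × (Day 7 improvement − 2), which gives about 15% to 21% missing

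The Day 7-based estimate regresses Day 14 on the earlier scores within arm and averages over all patients in that arm. This stands in for a likelihood-based model. A negative difference favours NAC.

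| Scenario, no true effect | Complete-case difference | t-test rejection | Day 7-based difference |
|---|---|---|---|
| b = 0.5 control, 0 test | −0.39 | about 19% | 0.00 |
| b = 0.25 control, 0 test | −0.18 | 7% to 8% | about 0 |
| b equal in both arms | about 0 | about 5% | about 0 |

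**5. Where the remedy falls short.** Keep b = 0.5 at control sites and 0 at test sites. If half the patients missing Day 14 also lack Day 7, the Day 7-based estimate keeps a bias of about −0.10; if all of them lack it, about −0.23. If non-return depends on Day 14 status itself, with the same slopes, the bias is about −0.39 even when Day 7 is complete.

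**The case against.** The strongest reply is that this is the least consequential analysis in the plan. It is optional, it sits under the secondary endpoints, and no conclusion is tied to it. Clustering is already handled where it matters most, by the required mixed model for the primary endpoint. That stands: a reader might infer that the plan has no cluster-adjusted estimate of the Day 14 difference, and the documents show otherwise. What the mixed model does not do, as described, is use Day 7 scores for patients without Day 14.

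A second reply is that neither the dropping of incomplete patients nor the absence of a centre effect is written down. This also stands. Both follow from the classical method and the synopsis's silence, and a fuller specification could remove them.

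Third, a reader might infer that investigators who know the arm decide who returns. The text says only that they set visits by medical condition. That can affect which scores exist, but nothing describes arm-dependent decisions.

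Fourth, the bias figures come from a chosen asymmetry, and the near-zero bias of the Day 7-based estimate follows from assuming Day 7 complete and missingness explained by it. This is correct, and step 5 of the working shows the limits. Also, an SD of 2.6 at each visit with a Day 0–14 correlation of 0.4 implies a change SD of 2.6 × √(2 × 0.6) = 2.85. The plan gives one SD and does not say whether it is per visit or for the change.

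**Conclusion.** The point holds as a cheap improvement to the plan, not as a fault that undermines the primary result. The only named analysis joining the three time points is an unspecified, optional ANOVA. As classically run, it discards incomplete patients and omits the randomised unit.

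At the planned ICC the cost of ignoring centre is small (about 6% against 5%). The 16% figure needs an ICC ten times the planned value.

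The bias of about 0.2 to 0.4 points, against a design difference of 1, requires non-return to depend on improvement in one arm and not the other. It is absent under the null when return behaviour is equal. A reader might take those figures as a forecast that the Day 14 comparison will favour NAC. The documents do not support that, because they give no data on who returns. They show only that open allocation, visits set by condition and 20% expected withdrawal leave room for it.

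**What to change.** Replace the optional Repeated Measures ANOVA, and extend the primary mixed model, with one pre-specified longitudinal mixed model:

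- **Outcomes:** Day 7 and Day 14 total scores, for every patient with at least one post-baseline score.
- **Fixed effects:** arm, visit, arm-by-visit and Day 0 total score.
- **Covariance:** unstructured within patient, with a random centre effect.
- **Inference:** small-sample degrees of freedom for 12 centres.
- **Reporting:** the Day 14 contrast as the cluster-adjusted estimate, and a table of Day 14 availability by arm and by Day 7 score.
- **Sensitivity:** an analysis in which missingness depends on the unseen Day 14 score.

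The cost is SAP wording and a little more modelling, with no new data and no change to the sample size. The main analysis would rest on a missing-at-random assumption given the Day 0 and Day 7 scores, and the gain shrinks where Day 7 is missing too. The availability table and the sensitivity analysis are therefore part of the fix.

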--	--

	
 Existence of rhinosinusitis complications. Adverse drug reaction related to NAC inhalation. Serious adverse events /adverse drug reactions.
Endpoints	
Primary Endpoint
 
 Change in the total score of the investigator’s symptomatic severity assessment (Day 0, Day 14) (Assessed symptoms: nasal congestion, nasal/postnasal discharge, facial pain/sense of facial pressure, reduction/loss of smell are rated in four categories [0=no symptom, 1=mild, 2=moderate, 3=severe]) 
Secondary Endpoint
 
 Change in the total score of the investigator’s symptomatic severity assessment (Day 0, Day 7) Change in the score of the investigator’s symptomatic severity assessment (Day 0, Day 7, Day 14) Change in SNOT-20 score (Day 0, Day 14) 
Safety Assessment Parameters
 
 Adverse drug reaction (ADR) related to NAC inhalation and incidences/profiles of serious adverse events and ADRs. Rate of subjects who discontinued the study due to ADR and relevant ADR profiles.

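### The optional Repeated Measures ANOVA lists Day 0 as an outcome level and does not say which term measures the treatment difference; a model of Day 7 and Day 14 adjusted for Day 0 would be clearer and more powerful

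*Combined protocol and SAP*

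**What the plan says.** The primary endpoint (Synopsis, Endpoints) is the change in the total score of the investigator's "symptomatic severity assessment (Day 0, Day 14"). The Day 7 secondary endpoint is the same change to Day 7.

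The required between-group analyses (Synopsis, Statistical Analysis Methods) are on change. They are a two-sample t-test at each of Day 14 and Day 7 and, for the primary endpoint, a mixed model that allows for clusters.

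The part on secondary endpoints then adds a supplementary and conditional analysis: "Repeated Measures ANOVA can be conducted to check inter-group difference taking into account of changes in the total score". The same sentence lists the visits that enter it, with the pre-treatment one among them: "symptomatic severity assessment on baseline (Day 0), Day 7 and Day 14". The text does not say whether the answer comes from the group main effect or from the group-by-time interaction. It gives no covariance structure, no centre term and no visit-specific contrast for this analysis.

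**The concern.** A two-group, three-visit Repeated Measures ANOVA produces two tests that could each be called the difference between groups.

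- **Group main effect.** This compares each arm's average over the three days. Day 0 precedes treatment, so it dilutes any later effect, and a difference already present at Day 0 counts as a group difference. The null hypothesis is equal mean level, whereas the endpoints concern equal change.
- **Group-by-time interaction.** This does test equality of change, but as a 2-df test of any difference in profile. It says nothing about size or direction at Day 7 or Day 14.

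This is the only stated analysis that uses the three visits together, so it may be reported as the result on symptom course. In an open study, where the analysis is run only if judged necessary, leaving the term unnamed allows the choice to be made after the data are seen. The two terms can give very different answers from the same data.

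**Working it through.** **Reproducing the plan's sample size.** Inputs from Sample Size and Rationale: "the assumed difference was 1 and the assumed standard deviation was 2.6"; "With the assumed intraclass correlation coefficient (ICC) of 0.005"; 5% significance (taken as two-sided) and 80% power; "6 clusters (study centers) per treatment arm with a total of 12 clusters and 20 subjects in each cluster".

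- Individually randomised: 2 × 2.6² × (1.96 + 0.84)² / 1² ≈ 106.1, so 107 per arm.
- Design effect: 1 + (20 − 1) × 0.005 = 1.095.
- 107 × 1.095 = 117.2 per arm, or 5.86 centres of 20, rounded up to 6 × 20 = 120. This matches "120 subjects will be required per treatment arm and 240 subjects in total". With 20% withdrawal, 240 / 0.8 = 300.

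**Assumptions not in the documents.** Compound symmetry; within-patient correlation ρ = 0.3, 0.5 or 0.7; 2.6 taken as the SD of change (the plan does not say whether it is the SD of score or of change); complete data; clustering ignored; Day 7 effect 0, 0.5 or 1. The per-visit SD is then s = 2.6 / √(2(1 − ρ)) = 2.20, 2.60 or 3.36.

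**Formulas, n = 120 per arm, so √(n/2) = √60.**

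- Test of Day 14 change: (1 / 2.6) × √60 = 2.98, power 84%.
- Group main effect: it estimates (0 + d7 + 1) / 3, where d7 is the Day 7 effect. The SD of a patient's three-visit mean is s√((1 + 2ρ)/3) = 1.61, 2.12 or 3.00. For d7 = 0.5 and ρ = 0.5: (0.5 / 2.12) × √60 ≈ 1.83, power 44%.
- Group-by-time: the noncentrality is 60 × Σ(dᵢ − d̄)² / (s²(1 − ρ)), and s²(1 − ρ) = 2.6² / 2 = 3.38 at every ρ. For effects 0, 0.5, 1 it is 60 × 0.5 / 3.38 = 8.9, power 76%. For 0, 0, 1 or 0, 1, 1 it is 60 × 0.667 / 3.38 = 11.8, power 88%.
- Day 14 score with Day 0 as covariate: residual SD s√(1 − ρ²) = 2.10, 2.25 or 2.40.

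**Power for a 1-point Day 14 effect, no baseline gap.**

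| Test | ρ = 0.3 | ρ = 0.5 | ρ = 0.7 |
|---|---|---|---|
| Group main effect, d7 = 0 | 36% | 23% | 14% |
| Group main effect, d7 = 0.5 | 67% | 44% | 25% |
| Group main effect, d7 = 1 | 89% | 68% | 40% |
| Group-by-time (2 df) | 76–88% | 76–88% | 76–88% |
| Test of Day 14 change | 84% | 84% | 84% |
| Day 14 adjusted for Day 0 | 96% | 93% | 90% |

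**Rejection when the arms change equally but differ by 0.5 point at all three visits.**

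| Test | ρ = 0.3 | ρ = 0.5 | ρ = 0.7 |
|---|---|---|---|
| Group main effect | 67% | 44% | 25% |
| Group-by-time | 5% | 5% | 5% |
| Test of Day 14 change | 5% | 5% | 5% |
| Day 14 adjusted for Day 0 | 25% | 14% | 8% |

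The last row follows because adjustment leaves a bias of 0.5(1 − ρ) = 0.35, 0.25 or 0.15.

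If the arms sit at −0.5 on Day 0, 0 on Day 7 and +0.5 on Day 14 (a true 1-point difference in change), the main effect estimates zero and rejects 5% of the time.

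Simulation at ρ = 0.5 (5,000 trials per scenario) agreed with the calculated figures for the three ANOVA and change tests to within about 1 point.

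**If 2.6 is the SD of the score.** At ρ = 0.3 the main effect has 27% to 77% power against 71% for the test of change. At ρ = 0.7 it has 20% to 60% against 97%. The ρ = 0.5 figures do not move.

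**The case against.** A reader might infer that the plan tests treatment with the group main effect, and so will miss a real Day 14 effect or declare one from a baseline gap alone. The documents do not support that. The sentence names no term, and its reference to changes in the score fits the group-by-time interaction at least as well; that term has correct size and reasonable power. The analysis is also conditional and supplementary. Every required between-group test is on change, and descriptive statistics of change by arm at Day 7 and Day 14 are already planned. These points stand, and they limit the concern to an unspecified term and a weaker method than the data allow.

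The size of the problem is also open to challenge:

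- The ρ = 0.7 column needs a Day 0 SD of 3.36. Inclusion criterion 4 confines Day 0 to scores 4 to 12, and a uniform spread over those nine values has SD √((9² − 1)/12) = 2.58. That column is therefore an extreme case if 2.6 is the SD of change.
- With the full effect present by Day 7 and ρ = 0.3, the main effect loses nothing (89% against 84%).
- Under the plan's own ICC, a persistent arm gap arising from centres has SD √(2 × 0.005 × 6.76 / 6) = 0.11, so 0.5 point is about 4.7 SDs. A gap that large needs a larger ICC or selective enrolment once the allocation is known. The latter is possible because centres and patients know it from the start, but the documents give no figure for it.

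What remains is that the text leaves the choice of term open, and that neither term gives a treatment estimate at a stated visit.

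**Conclusion.** The point holds as a specification gap with an inexpensive improvement. It is not an error in the primary analysis, and the required t-tests and mixed model on change are untouched.

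Read as the group main effect, the analysis answers a different question from the endpoints. Its power is about 14% to 89% against 84% for the test of change, and rejection is 25% to 67% under a constant 0.5-point gap. Read as the interaction, it is valid (5% size, 76% to 88% power) but gives no visit-specific estimate. Adjusting for Day 0 gives about 90% to 96% at Day 14.

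The algebra about what the main effect tests needs no assumption. The percentages rest on the assumed correlation, Day 7 effect, compound symmetry and reading of 2.6 as the SD of change, with clustering ignored. The lower end of the power range comes from the least plausible correlation.

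**What to change.** In Analysis of secondary endpoints, replace the Repeated Measures ANOVA sentence so that, if a longitudinal analysis is run:

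- the outcomes are the Day 7 and Day 14 total scores (or changes from Day 0), with Day 0 removed from the repeated levels;
- the terms are Day 0 score as covariate, treatment, visit and treatment-by-visit, with study centre as a random effect;
- the results are the treatment contrasts at Day 14 and Day 7, each with a 95% CI;
- the contrast in change from Day 0 is shown beside them.

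If Repeated Measures ANOVA is kept, state that only the group-by-time contrasts for change from Day 0 are interpreted, and that a group main effect including Day 0 is not reported as evidence on treatment. Also state whether the outcome is the score or the change, since change at Day 0 is zero by definition.

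The cost is SAP wording only. No new data, visits or patients are needed, and inclusion criterion 4 already requires a Day 0 score. The downside is that, with a real persistent baseline gap, the covariate form is itself partly sensitive (about 8% to 25% rejection for a 0.5-point gap), which is why the change contrast should accompany it.

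### The SNOT-20 plan, read naturally, t-tests each item as well as the total between arms with no ranking or adjustment; test only the total and describe the items

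*Combined protocol and SAP*

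**What the plan says.** The Endpoints section of the synopsis lists one SNOT-20 secondary endpoint: "Change in SNOT-20 score (Day 0, Day 14"). The instrument is patient-completed; the Study Methodology section lists "SNOT-20 (Sino-Nasal Outcome Test) assessment: to be filled-out by subjects".

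Under Statistical Analysis Methods, analysis of secondary endpoints, the SNOT-20 bullet has two sentences. The first asks for descriptive statistics on "individual and total SNOT-20 scores by group on Day 14 compared with each time point and baseline (Day 0"). The second reads: "Paired t-test shall be used to check intra-group change difference and Two sample t-test shall be used to check inter-group change difference". It does not say which of the scores just named are to be tested.

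The documents give no multiplicity adjustment, no order of testing and no exploratory label for item results. The 5% level appears only in the sample size rationale for the primary endpoint. The mixed model that accounts for study centres is specified only for the primary total symptom score, so the SNOT-20 comparison rests on ordinary t-tests in a trial randomized by centre.

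**The concern.** The two sentences sit under one bullet, and the second is mandatory, whereas the repeated-measures ANOVA and the regression described just before it are optional. The natural reading is that each item and the total receive the same tests. That gives about 20 between-arm item comparisons for an endpoint listed once, all with equal standing.

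Both investigators and subjects know the allocation from the start, and subjects complete the questionnaire themselves. The synopsis also says that clinical data on NAC inhalation are scarce. An isolated significant item could therefore be quoted as evidence of benefit even though the SNOT-20 total shows none, and nothing in the plan tells the reader how much weight such an item deserves.

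**Working it through.** **Inputs.** From the sample size rationale: "the assumed difference was 1 and the assumed standard deviation was 2.6"; "With the assumed intraclass correlation coefficient (ICC) of 0.005, significance level of 5%, and test power of 80"%; and "6 clusters (study centers) per treatment arm with a total of 12 clusters and 20 subjects in each cluster". Allocation is "test sites : control sites =1:1", by centre. Assumed, because the documents do not give them: 20 items (from the instrument's name), two-sided testing, and the correlation between items.

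**The plan's own figure.** Before clustering, n per arm = 2 × [2.6 × (1.960 + 0.842)]² / 1² = 106.1. The design effect is 1 + (20 − 1) × 0.005 = 1.095. Then 106.1 × 1.095 = 116.2 per arm, or 5.8 clusters of 20, rounded up to 6 × 20 = 120. With 20% withdrawal, 240 / 0.8 = 300. The stated sample size reproduces.

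**Counting the tests.** 20 items + 1 total = 21 scores. Each has one paired test in each of two arms and one two-sample test, so 21 × 3 = 63 tests: 42 within-arm and 21 between-arm. Only the between-arm tests estimate a NAC effect. Both arms receive standard treatment for a symptomatic acute illness, so a within-arm fall from Day 0 to Day 14 may be real without any NAC effect. The family at issue is the 20 between-arm item tests.

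**False-positive risk, each test at exactly 5%.** Expected false items = 20 × 0.05 = 1. If items are independent, the chance of at least one is 1 − 0.95²⁰ = 64%. For correlated items, 200,000 sets of 20 equally correlated null z-statistics were simulated and compared with ±1.96, taking the total as their standardized sum.

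**With clustering ignored.** At ICC 0.005 the variance is 1.095 times what the t-test assumes. The error per test is 2 × [1 − Φ(1.96/√1.095)] = 6.1%, and the same simulation was repeated with that inflation.

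| Assumed inter-item correlation | At least one significant item, 5% per test | A significant item but a non-significant total, 5% per test | At least one significant item, clustering ignored (ICC 0.005) |
|---|---|---|---|
| 0 | 64% | 60% | 72% |
| 0.3 | 54% | 49% | 62% |
| 0.5 | 42% | 37% | 48% |
| 0.7 | 29% | 24% | 34% |

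**After the change.** One between-arm SNOT-20 test remains, at a nominal 5% provided that it accounts for clusters. With a plain t-test even that single test runs at 6.1% at ICC 0.005, or about 16% at an assumed ICC of 0.05 (design effect 1 + 19 × 0.05 = 1.95). If the sponsor prefers to keep all 21 between-arm tests, Bonferroni gives 0.05 / 21 = 0.0024 each.

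**The case against.** The test sentence does not name the items. The same sentence is used elsewhere in the section for single total scores, so the items may be meant only for description. That is possible, but the text does not say it, and a statistician following the text would test every score named. If description is the intention, the same clarification settles it.

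The Endpoints section says score rather than total score, while neighbouring bullets draw that distinction. It is therefore a reading, not a stated fact, that the endpoint is the total alone. This stands. The plan needs to say which score is meant.

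A reader might infer that all 63 tests are exposed to false positives if NAC does nothing. The documents do not support that: 42 of the tests are within-arm, and a significant one may be a true result about change over time. It would mislead only if read as evidence for NAC.

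A reader might also infer that a false item finding is likely. That depends on a correlation the documents do not give. With 5% per test the chance is already below one half at a correlation of 0.5 (42%); with clustering ignored at the plan's ICC it is 55% at 0.4 and 48% at 0.5.

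Finally, no item-level claim is planned. SNOT-20 is a secondary endpoint in a study the sponsor describes as observational, and an unadjusted p-value becomes a false claim only if someone reports it as a finding. This is fair and keeps the point minor. It does not remove the case for saying beforehand how items will be used.

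**Conclusion.** The point holds as a minor one. Followed as naturally read, the plan produces about 20 unranked, unadjusted between-arm item tests. With no NAC effect, the chance of at least one nominally significant item is about 29% to 64% across assumed correlations of 0.7 to 0, or about 34% to 72% when clustering is ignored at the plan's ICC with 20 per cluster. These ranges rest on 20 items, equal correlation among them, two-sided 5% tests and a normal approximation.

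The documents do not support saying that false item claims are probable or that the sponsor intends to make any. What they show is an unrestricted test rule and no statement of the standing of item results. The primary endpoint and the sample size are not affected.

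**What to change.** In the SNOT-20 bullet of Statistical Analysis Methods:

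- Name the SNOT-20 total, change from Day 0 to Day 14, as the only SNOT-20 score tested between arms, and word the Endpoints entry to match.
- Test it with the cluster-aware mixed model already planned for the primary endpoint. Restricting the t-test to the total would not by itself hold the error at 5%.
- Report the items by arm descriptively (means, changes, and confidence intervals if wanted), with no p-values and no conclusions from single items.

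The cost is a short wording change and one additional fit of a model already in the plan. Item-level p-values are lost. Data collection, the primary endpoint and the sample size stay as they are.
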